3.4 Outcome measurement

The primary clinical outcome is the reported number of episodes of sore throat in the two years after randomisation.

Secondary clinical outcomes include reported number of episodes of sore throat, otitis media and upper respiratory tract infection which invoke a GP consultation; reported number of symptom-free days; reported severity of sore throats and surgical and anaesthetic morbidity. In addition to the measurement of these clinical outcomes, the impact of the treatment on costs and quality of life will be assessed. There will also be an economic evaluation.

4 Subject selection

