9.1 Data to be collected

All participants will be followed-up for 24 months from the date of initial randomisation. To minimise recall bias, data on sore throats will be gathered by a simple, structured daily health diary completed and returned by participants on a monthly basis for 24 months. Experience of similar studies suggests that with appropriate telephone reminders 90% of diaries will be returned completed.

In addition simple outcome questionnaires will be administered to trial and cohort study participants. Overall we anticipate an 80% response rate. Interview surveys will be done at 3, 12 and 24 months after randomisation. A baseline questionnaire will be completed by all participants upon recruitment to the trial. The greater frequency of data collection in the first 12 months is necessary in order to capture data on expected changes in direct and social costs to participants in the first 12 months. Experience also suggests that data on consultation rates and prescribed medication can be gathered most accurately and reliably from medical records. Manual abstraction will be performed by trained research nurses at the end of follow up for all participants

| Primary clinical outcome | Measurement method | When | Where |
|---|---|---|---|
| Number of events of recurrent sore throat | Self-completed diary (by parent or child) | Daily recording but collected four-weekly for 24 months | Participants' homes |
| Secondary clinical outcomes | Measurement method | When | Where |
| Number of events of recurrent sore throat, otitis media or URTI recorded by GPs | GP records | End of 24 month follow-up period | General practices (GP records) |
| Adverse events: re-referral for tonsillectomy; number of symptom-free days | Self-completed diary (by parent or child) and GP records | Daily recording but collected four-weekly for 24 months and end of 24 month follow-up period | Participants' homes (diary) and general practices (GP records) |

Table 1 Clinical outcome measures for trial and cohort studies

Table 2 Measuring treatment impact

| Impact | Measure | When | Where |
|---|--|-------------------------------------|--------------------|
| Costs to participants of the condition and its management | Questionnaire to children and parents | Base-line, 3, 12 and 24 months | Participant's home |
| Social costs: e.g. time off school and parental time off work | Self-completed diary (by parent or child) | Base-line, 3, 12 and 24 months | Participant's home |

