9.1.1.2 Measure of benefits used and study type

Cost consequences analysis (CCA), cost-effectiveness analysis (CEA) and cost utility analysis (CUA) will be conducted. In CCA, all the outcomes used in the clinical study will be adopted as measures of benefits, including the QoL dimensions. In CEA, the benefits will be measured by the number of events of recurrent sore throat and the number of symptom-free days. In CUA, different health outcomes will be combined with QoL dimensions.

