10.2 Statistical analysis

10.2.1 Main analysis

An intention to treat analysis will be performed. In particular, children randomised to nonsurgical conventional medical treatment will be retained in that group for the analysis even if they subsequently receive a tonsillectomy.

The primary clinical outcome measure will be the number of episodes of sore throat. This variable will be analysed using generalised linear modelling assuming a Poisson error structure with a log link function⁵¹. By fitting the difference between the two experimental groups as a fixed effect, interval estimates of the effect of tonsillectomy (in each of the first two years of follow up) will be generated. These estimates will then be used in the economic analysis.

The same approach will be used to analyse the other outcomes. A Poisson error structure will be assumed for data in the form or a count (such as the number of episodes of absence from school) and normal error structure adopted for continuous variables (such as the quality of life indices).

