12.3 Assessment of safety

Adverse events will be recorded by self completion daily diaries (parent or child) which will be collected four weekly and GP records which will be examined at the end of the 24 months follow up period. Expected adverse events include infection, haemorrhage and pain following tonsillectomy with possible hospital readmission as well as sore throat, nausea, fever and dysphagia.

For the purposes of this study no reporting of serious adverse events is required. All adverse events will be managed as per normal care, since the intervention process of this study does not deviate from normal care.

13 Ethical considerations

The conduct of this study will be in accordance with the ethical principles set out in the Declaration of Helsinki.

The trial has approval from MREC and all the associated LRECs. The trial also holds a Clinical Trial Authorisation from the MHRA. The trial has NHS R&D and Caldicott Guardian approval from each participating site. There are no particular ethical problems with this trial. The ethical challenge is as with any surgical randomised trial where one arm is an irreversible procedure under general anaesthesia and the other limb effectively maintenance of the status quo with reverting to surgery an outstanding choice. Set against the surgical risk, however, is the essentially 'curative' nature of the intervention – no tonsillitis can occur once the tonsils have been removed. Further, the children under consideration all have qualifying levels of sore throat and would otherwise be eligible for surgery. In other words the issue is more the withholding of tonsillectomy rather than one of random allocation to intervention.

All subjects will provide written informed consent before any study procedures are carried out and a participant information sheet will be provided. As part of the consent process participants must agree to researchers & regulatory representatives having access to their medical records. Participants will also be informed that they have the right to withdraw from the study at any time.

14 Financing and insurance

The NHS Trust has liability for clinical negligence that harms individuals toward whom they have a duty of care. NHS Indemnity covers NHS staff and medical academic staff with honorary contracts conducting the trial.

15 Reporting and dissemination

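### A by-arm contrast of surgical morbidity understates the per-operation risk when controls have surgery; separately, Table 1 lists re-referral for tonsillectomy as an adverse event

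*Protocol*

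**What the plan says.** Section 3.4 of the protocol includes among the secondary clinical outcomes "reported severity of sore throats and surgical and anaesthetic morbidity".

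Section 10.2.1 sets intention to treat and spells out what this means for crossovers: "children randomised to nonsurgical conventional medical treatment will be retained in that group for the analysis even if they subsequently receive a tonsillectomy". The treatment effect comes from a Poisson model with a log link, "By fitting the difference between the two experimental groups as a fixed effect". The section then says: "The same approach will be used to analyse the other outcomes". It makes no exception for surgical harm, and no section of the protocol provides a summary by operation received.

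Table 1 in section 9.1 has a row that reads "Adverse events: re-referral for tonsillectomy; number of symptom-free days". It has no row for surgical and anaesthetic morbidity. Section 12.3 describes adverse events differently: "Expected adverse events include infection, haemorrhage and pain following tonsillectomy with possible hospital readmission". It adds sore throat, nausea, fever and dysphagia, and does not mention re-referral. Section 13 says that children in the non-surgical arm can still turn to surgery.

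**The concern.** Intention to treat answers what follows from a policy of offering surgery or medical care. It does not answer what the operation itself risks. Surgical and anaesthetic morbidity exists only where there was an operation, so a control child who is operated on and bleeds counts in the control arm and narrows the difference between arms. A reader who takes that difference as the risk of tonsillectomy will take it as too small. Families and clinicians weighing benefit against risk need the figure per operation, and the protocol does not plan one for the trial children.

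Re-referral is a second, separate matter. A child whose tonsils have been removed has hardly any reason to be referred for tonsillectomy again, so the item falls almost wholly on controls. It shows that medical care was judged insufficient or that the family chose surgery. Counted as an adverse event, it adds to the control arm's tally something that is not a harm. It could also enter the cost-consequences analysis on that footing, since section 9.1.1.2 says: "In CCA, all the outcomes used in the clinical study will be adopted as measures of benefits".

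**Working it through.** **Inputs**
- Haemorrhage risk per operation, h = 2.15%; overall complication rate 8% to 14% (section 1.2).
- Share of controls operated on, c: no figure for this trial. Section 1.3 reports 1 in 3 in an earlier trial. I show 10% to 50% as an assumed range.
- Share of the surgery arm operated on, u: no figure given. I take 1, with 0.9 as an assumed variant.
- 142 children per arm (section 10.1); 406 recruited, or 203 per arm (section 4.3).
- Assumption: no such complication without an operation.

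**The plan's own figures.** The protocol states none for harm. Its sample size reproduces: 2 x (1.96 + 0.8416)² x 4.5² / 1.5² = 2 x 7.849 x 9 = 141.3, so 142 per arm. Then 284 / (1 - 0.30) = 405.7, so 406.

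**What the by-arm contrast estimates.** The surgery-arm rate is h x u and the control-arm rate is h x c. The difference is h(u - c). On the log-link scale of section 10.2.1 the ratio is u / c, in which h cancels, so that ratio reflects uptake and crossover and not the risk of the operation.

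Haemorrhage, h = 2.15%, u = 1:

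| c | Surgery arm | Control arm | Difference (points) | Share of h | Ratio |
|---|---|---|---|---|---|
| 10% | 2.15% | 0.22% | 1.94 | 90% | 10 |
| 20% | 2.15% | 0.43% | 1.72 | 80% | 5 |
| 1 in 3 | 2.15% | 0.72% | 1.43 | 67% | 3 |
| 50% | 2.15% | 1.08% | 1.08 | 50% | 2 |

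The surgery-arm column does not move with crossover. It falls only with non-uptake: at u = 0.9 it is 0.9 x 2.15 = 1.94%, and with c = 1 in 3 the difference is 2.15 x (0.9 - 0.333) = 1.22 points, 57% of h.

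For overall complications of 8% to 14%, u = 1 and c = 1 in 3 give 8 x 2/3 = 5.3 to 14 x 2/3 = 9.3 points. The assumption of no background events is weaker here, because many of these complications are minor symptoms that unoperated children also have.

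**Expected counts at c = 1 in 3.** With 142 per arm: 142 x 0.0215 = 3.05 bleeds in the surgery arm and 142/3 x 0.0215 = 1.02 in the control arm. The control arm holds 1.02 / 4.07 = 25% of them. If all 203 per arm were observed, the counts are 4.4 and 1.5.

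**Precision.** At 3.05 against 1.02 bleeds, the log ratio has a standard error of √(1/3.05 + 1/1.02) = 1.14. The 95% interval around a ratio of 3 is a factor of exp(1.96 x 1.14), about 9.4, either way: roughly 0.32 to 28. On the difference scale the standard error is √4.07 / 142 = 1.42 points, as large as the difference of 1.43. Counting per operation gives 4.07 bleeds in 142 + 47.3 = 189.3 operations, which is 2.15% with a standard error of √4.07 / 189.3 = 1.07 points. That is still imprecise, but it addresses the right quantity.

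**Re-referral.** Table 1 places it under adverse events. The secondary outcomes in section 3.4 and the expected adverse events in section 12.3 both leave it out. The passages do not agree on what it is.

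**The case against.** The strongest reply is that the by-arm analysis of harm is read out of one general sentence. Its examples are school absence and quality of life, and no section describes a harm analysis as such. A statistical analysis plan, which is not shown, may already contain a summary by treatment received. This limits the weight of the point but does not remove it. The sentence covers the other outcomes without exception, surgical morbidity is one of them, and even if only the model carries over, the fitted contrast is still between arms.

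Some stronger readings are tempting, and the documents do not support them:
- A reader might infer that the surgery arm's own complication rate is understated. Control crossover leaves it unchanged; only allocated children who are not operated on lower it.
- A reader might infer that calling re-referral an adverse event moves bleeds into the control arm. It moves none. The label may also be loose, since the same row names symptom-free days, which are plainly not an adverse event.
- A reader might infer double counting in the cost-consequences analysis. Such an analysis lists outcomes side by side, and section 9.1.1.2 adds nothing together.
- A reader might infer that the dilution runs through the economic evaluation. Section 9.1.1.4 takes resource, cost and impact data on surgical complications from outside the trial, so it need not.
- A reader might want the by-arm comparison dropped. Sore throat, nausea and fever also occur in unoperated children, and for these the randomised comparator is needed.

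Two further points stand. Intention to treat is right for effectiveness and legitimate for the policy question. It also dilutes the benefit of surgery, so an undiluted per-operation harm beside a diluted benefit needs a label. The surgical cohort (sections 3.2 and 10.2.4) does give harm in operated children, but they are children who declined randomisation, not the operated trial children.

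**Conclusion.** The point holds in a limited form. Followed as written, section 10.2.1 yields a between-arm contrast of surgical morbidity that lies below the per-operation risk whenever controls are operated on. For haemorrhage, with full uptake, it is 1.94 to 1.08 points against 2.15 over an assumed crossover of 10% to 50%. The direction is certain once any control child has surgery. The size is not known: the 1 in 3 is borrowed from an earlier trial in more severely affected children, and the calculation assumes equal risk per operation in both arms and no background events. With about 3 bleeds against 1, the contrast is also too imprecise to inform anyone.

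The listing of re-referral as an adverse event is a separate inconsistency between Table 1 and section 12.3. It bears on how the control arm's adverse events are counted, not on the bleeding rates.

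**What to change.** 1. In section 10.2.1, keep the intention-to-treat comparison and add a summary of surgical and anaesthetic morbidity per operation performed, in all operated trial children whichever arm they were in, with exact confidence intervals and the surgical cohort alongside. Label it as non-randomised, and leave non-specific symptoms to the by-arm comparison.
2. In Table 1, take re-referral out of the adverse events, so that the table and section 12.3 agree. Report it as crossover or treatment failure, together with the number of operations done in controls and not done in the surgery arm. If it appears in the cost-consequences analysis, it should carry the same label.

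Both are changes of wording and need no new data. The cost is one extra non-randomised table, which readers must be told not to set directly against the intention-to-treat benefit.

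### The rule in section 10.2.1 that every count gets Poisson errors ties the standard error of symptom-free days to the number of well days, not to the variation in symptom days

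*Protocol*

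**What the plan says.** Protocol section 10.2.1 analyses the primary outcome by "generalised linear modelling assuming a Poisson error structure with a log link function". It then says "The same approach will be used to analyse the other outcomes", and divides those outcomes in two: "A Poisson error structure will be assumed for data in the form or a count", and normal errors for continuous variables, with the quality of life indices as the example. No exception, dispersion parameter, upper bound or exposure term is stated.

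Section 3.4 lists "reported number of symptom-free days" among the secondary clinical outcomes, and Table 1 takes it from the daily diary and GP records. Section 9.1.1.2 gives it a second role: in the cost-effectiveness analysis "the benefits will be measured by the number of events of recurrent sore throat and the number of symptom-free days". On the time frame, section 9.1 says "All participants will be followed-up for 24 months from the date of initial randomisation", and it expects 90% of diaries to come back completed.

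**The concern.** Symptom-free days are a whole number of days, so as written they fall under the count rule. They are not the kind of count for which a Poisson variance is plausible. Over a fixed period, well days are the period minus ill days. Their spread between children is therefore exactly the spread in ill days. A Poisson model ignores this and takes the variance to be the mean number of well days, a large number that says little about how much children differ.

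At stake are the confidence interval and test for this outcome. They matter beyond the secondary results because section 9.1.1.5 makes statistical significance a switch: depending on the outcome measure, if no strategy is significantly more effective, a cost-minimisation framework applies and the cheaper care is recommended.

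**Working it through.** **The plan's own figures.** The protocol gives no variance or power figure for symptom-free days. Its sample size rests on missed schooling: 2 × (1.96 + 0.842)² × 4.5² / 1.5² = 141.3, so 142 per arm, as stated in section 10.1. The present point does not affect it.

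**Inputs**
- Follow-up of 24 months, about 730 days (section 9.1).
- SD of sore throats per year 2.0, and 142 children per arm (section 10.1).
- Days per episode: 5 (the guideline criterion in section 1.1) to 10 (top of health state X, Appendix 2). Neither is a forecast for this trial, so the range is an assumption.
- Correlation between a child's two yearly counts: not given; assumed 0 to 1.
- Mean symptom days over two years: assumed 30 (3 episodes × 5 days × 2 years) to about 90, giving means of 700 to 640 symptom-free days.

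**1. Two-year SD of episodes.** Correlation 0: √(2.0² + 2.0²) = 2.83. Correlation 1: 2.0 + 2.0 = 4.0.

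**2. True SD of symptom-free days** (equal to that of symptom days, complete diaries, fixed duration). Low: 5 × 2.83 = 14.1. High: 10 × 4.0 = 40.

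**3. SD implied by the Poisson rule.** √700 = 26.5; √640 = 25.3.

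**4. Ratio of Poisson to true standard error.** Low spread: 25.3/14.1 = 1.79 to 26.5/14.1 = 1.87. High spread: 25.3/40 = 0.63 to 26.5/40 = 0.66.

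A single-year analysis needs no correlation assumption. With three 5-day episodes, √350 = 18.7 against 5 × 2.0 = 10, ratio 1.87. With three 10-day episodes, √335 = 18.3 against 10 × 2.0 = 20, ratio 0.92.

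**5. Milder case with varying durations.** Take 3 episodes a year of 5 days, with duration CV either 0 or 0.5. Variance = Var(N)·d² + E(N)·Var(d). With CV 0.5 and correlation 0: 8 × 25 + 6 × 6.25 = 237.5, SD 15.4. With CV 0.5 and correlation 1: 16 × 25 + 37.5 = 437.5, SD 20.9. Across the case the Poisson standard error is about 1.3 to 1.9 times too large. A null simulation (142 per arm, complete diaries, fixed 5-day episodes, independent years, 2,000 runs) rejected in 0.0% of runs at the 5% level, with variance/mean about 0.29.

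**6. Coherence.** Take arm means of 690 and 700 symptom-free days, which are the same data as 40 and 30 symptom days, with 142 per arm.
- As well days: ln(700/690) / √(1/97,980 + 1/99,400) = 0.01439/0.00450 = 3.2.
- As ill days: ln(40/30) / √(1/5,680 + 1/4,260) = 0.2877/0.0203 = 14.2.

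The same rule gives two very different answers from one data set. Neither is right: with a true SD of 14.1 to 40 the standard error of the difference is SD × √(2/142), i.e. 1.68 to 4.75 days, so z for 10 days is about 6.0 to 2.1.

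**7. Effect on the economic switch.** At a mean of 700 the Poisson standard error of the difference is √(2 × 700/142) = 3.14 days. If the true SD is 14.1, a 6-day gain has z = 6/1.68 = 3.6, but the rule gives 6/3.14 = 1.9, below 1.96. Section 9.1.1.5 would then apply cost-minimisation on this measure.

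**8. Diaries, conditional on raw totals without an exposure term.** At 90% return, 0.10 × 730 = 73 diary days per child are unobserved over two years. Return of 92.5% against 87.5% with no treatment effect gives (0.925 − 0.875) × 700 = 35 days of false difference, rejected in all 2,000 simulated runs.

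**The case against.** **Missing diaries.** A reader might infer that the Poisson rule counts unreturned diaries as days with symptoms. The protocol does not support this. Nowhere does it say that such days are scored as symptomatic or that raw totals are modelled. A log offset for days observed is fully compatible with a Poisson model, and such detail may sit in a statistical analysis plan. Equal return in both arms would also leave the ratio under a log link unbiased. Nor should the 73 unobserved days, a two-year figure, be set against one year of health state X (42 to 70 days); over two years that state implies 84 to 140. What stands is conditional: if raw totals were used, unequal return would bias the comparison.

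**Overdispersion.** A reader might also think that a dispersion parameter would not help because the variable has a ceiling. It would: an estimated dispersion, which may fall below 1, or a robust variance corrects the standard error of a two-arm comparison. The denominator would be the only thing left to settle. The objection is thus to the Poisson variance as stated, not to every log-link model.

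**Inputs.** The SD range is not simply the protocol's own. Duration and between-year correlation are assumed, and the too-small end needs long episodes with strong correlation between years. That is fair. It limits the claim about direction, not the mismatch.

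**Economics.** A wrong Poisson variance does not bias the arm means, so with complete diaries the incremental ratio keeps its point estimate. Section 9.1.1.6 also plans intervals for the ratios. The significance switch in section 9.1.1.5 remains, and that is where the harm can enter.

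**Scope.** Section 10.2.1 names episodes of school absence, not symptom-free days, as its example of a count. But it offers only two classes, and a number of days belongs to the first.

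**Conclusion.** The point holds for the standard error. As written, the rule gives symptom-free days a variance of about 640 to 700, while with complete diaries the true variance is that of symptom days. Under the stated assumptions the standard error runs from about 1.8 times too large to about 0.65 of the true size. In the milder case it is too large, so a real gain may be missed. The direction in this trial cannot be fixed from the protocol.

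The missing-diary part is a conditional warning only: no exposure term is stated, and the bias arises if raw totals are modelled and return differs between arms. The primary outcome and the sample size are untouched. The change is worth making because the stated model is wrong for an outcome that can steer the economic recommendation.

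**What to change.** In section 10.2.1, except symptom-free days from the Poisson rule. Model symptom days out of diary days returned, using either a log offset for days returned or a binomial denominator, with a robust or estimated-dispersion variance. The variance allowance is needed in either form: a plain binomial with 30 symptom days in 730 gives SD √(730 × 30/730 × 700/730) = 5.4, against at least 14 here, and step 6 shows what a plain Poisson model of symptom days does. The binomial form with a logit link has the advantage of giving the same answer for well and ill days.

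For reporting and for the cost-effectiveness analysis, convert to symptom-free days per year as 365 × (1 − fitted proportion of days with symptoms), with the interval carried through, and use that interval where section 9.1.1.5 asks about significance.

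The cost is a few sentences of analysis wording. Diaries, follow-up and sample size do not change.
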